3 STUDY PLAN

3.1 Study Design

This is a Phase III, double-blind, placebo-controlled, multicenter, randomized study of pracinostat in combination with azacitidine (AZA) in patients ≥ 18 years of age with newly diagnosed acute myeloid leukemia (AML) not fit to receive intensive induction chemotherapy.

A maximum of 500 patients are planned to be enrolled over a period of approximately 30 months at approximately 130 study centers. Patients who meet the eligibility criteria and consent to participate will be randomized 1:1 to Group A (experimental group) or Group B (control group). Randomization will be stratified by cytogenetic risk category (intermediate vs. unfavorable risk) and ECOG Performance Status (0-1 vs. 2).

Study treatment, defined as the treatment with pracinostat/placebo (study drug) in addition to the background therapy (AZA), will continue until there is documented disease progression or relapse from CR while receiving study treatment, or non-manageable toxicity. There is no upper limit to the number of treatment cycles administered, and study treatment should be continued as long as patients derive a clinical benefit.

In the Phase II study MEI-004, 6 patients (12%) required more than 6 cycles of pracinostat + AZA to achieve a CR. It is recommended, therefore, that patients who have no evidence of disease progression should receive a minimum of 6 cycles of study treatment to allow adequate exposure to study drug and background therapy before considering a switch to other therapies.

[figure not shown]
Once permanently discontinued from study treatment, patients will be followed for AEs (for 30 days) and then they will enter the Long-term Follow-up phase of the study (Section 5.2). Patients in the Long-term Follow-up phase of the study will be followed every 3 months (± 1 month) for documentation of disease progression, if applicable, and overall survival. Patients will be followed until death or until end of this study (refer to Section 3.2 for end of this study definition).

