9.2 Randomization and Stratification

This study will employ a 1:1 randomization. Patients will be stratified based on the following factors:

- Cytogenetic risk category (intermediate vs. unfavorable-risk)
- ECOG 0/1 vs. 2

Information on pracinostat + AZA (Phase 2 study MEI-004) suggests some factors as influencing the OS. This information was combined with information provided by current literature on AZA [[Dombret, 2015](#)] and the most influencing factors emerged as candidates chosen as stratification factors at randomization to guarantee a proper balance between treatments. In particular ECOG was selected as grade 2 is generally much less frequent than grades 0/1, while Cytogenetic risk was included as showing a large difference between intermediate and unfavorable risk.

If available, the central cytogenetic test result will be used to assess the cytogenetic risk category at randomization. If the central result is not available, the local result will be used.

Randomization will be conducted centrally via an IWRS.

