3.3 SAMPLE SIZE CONSIDERATIONS

This is an event-driven study. Sample size was computed for a group-sequential design with stopping rules for both futility and superiority (study-wise one-sided alpha level=0.025, power 0.90) with one interim analysis at 67% (2/3) of information and a final analysis. The alpha error spending function is from the O'Brien Fleming function for superiority and the Gamma family (with $\gamma=-5.4695$, more conservative than O'Brien Fleming) for futility (non-binding). Proportionality of hazards is assumed. Assuming that median OS is 10.0 months in the Group B (placebo + AZA) the aim is to detect, by means of the log-rank test or equivalent, an increase to 14.0 months in Group A (pracinostat + AZA), i.e. a HR of 0.714286. A total of 390 events (deaths) allows to meet a power requirement of at least 90% (actually 90.87%; it was 90% with the original function used in v1 protocol; further calculations kept fixed the number of events needed) at a study-wise one-sided significance level of 0.025.

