5.5 SIGNIFICANCE LEVEL

The overall significance level for the primary efficacy endpoint is 0.025 (one sided). As an interim analysis according to the O'Brien Fleming function for superiority and the Gamma family function (with $\gamma=-5.4695$ for non-binding futility) will be done after 260 events (2/3 of the total number of events), the respective significance levels are 0.00605 for the interim and 0.02314 for the final analysis. These significance levels will be re-computed at time of analysis based on the real fraction of information available.

Calculations of significance levels and related thresholds were performed by means of SAS PROC SEQDESIGN.

The following table shows probabilities to stop at interim analysis for futility or superiority with the null and alternative hypotheses for the primary endpoint:

Table 1 Probability to stop at Interim Analysis HA as Median OS	10 months	14 months
Gamma spending function $\gamma=-5.4695$ for futility	0.70094	0.01442
O'Brien Fleming for superiority	0.00605	0.58059

The following table shows probabilities of significant results for the first secondary endpoint, according to the chosen hierarchical procedure and assuming no need to consider the correction for multiplicity as 100% of information would be collected (which was the assumption at time of SAP V1). The reference alternative hypothesis is that the difference between treatments in the CR rate is 0.13 (having 0.20 as the rate for the placebo group). Probabilities are corrected by unconditional probability of significant results for the primary endpoint as conditional probability assumes the correlation between endpoints to be known. The obtained results are conservative and represent the lower probability bound assuming no correlation.

Table 2		
Secondary endpoint(s)		
Assumption: 100% information for secondary endpoint at interim analysis is available		
probability of significant results	0.13 rate difference	
	Independent from primary endpoint (i.e. as it was the only endpoint in the study)	Hierarchical procedure *
at Interim Analysis	0.91	0.55
Overall	0.91	0.82

* rounded power for the primary endpoint is 0.90 overall and 0.60 at interim analysis, respectively (median OS = 14 months vs. 10 months)

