9.2.2 Treatment emergent adverse events (TEAEs)

Treatment-emergent AEs (TEAEs) are defined as AEs with onset date/time at or after the start date/time of the first intake of pracinostat /placebo, or AEs with onset date/time prior to start date/time of the first intake of pracinostat/placebo that worsen in severity after the start date/time of the first intake of pracinostat /placebo, up to the end of the observation period. The observation period is defined as 30 days after the last dose of pracinostat/placebo or start of a new therapy for AML, whichever occurs first. TEAEs will be summarized by treatment group.

Where dates and/or times are missing or partially missing, AEs will be considered treatment emergent, unless there is clear evidence (through comparison of partial dates and/or times) to suggest that the AE started prior or after the study period.

The following tables will be produced:

- An overview summary of TEAEs by treatment group, including counts and percentages of patients as well as the number of events. The summary includes the following kinds of AEs:
 - any TEAE;
 - TEAEs by worst NCI CTCAE grade (only number of patients and %)
 - TEAEs by NCI CTCAE grade
 - TEAEs causally related to study drug / AZA / study drug or AZA (i.e either component of the study treatment);
 - TEAEs leading to permanent discontinuation of study treatment;
 - TEAEs leading to interruption of study treatment (separately for study drug and AZA)
 - TEAEs leading to dose reduction
 - SAEs;
 - SAEs causally related to study drug / AZA / study drug or AZA;
 - fatal SAEs;
 - fatal SAEs causally related to study drug / AZA / study drug or AZA
 - TEAEs of special interest
 - TEAEs of special interest related to study drug
- The number and percentage of patients reporting TEAEs will be provided by treatment group, System Organ Class (SOC), Preferred Term (PT), worst NCI CTCAE grade, and total. TEAEs will be sorted by SOC and PT in alphabetical order (SOC and PT within SOC).
- The number and percentage of patients reporting TEAEs together with the number of AEs, will be provided by treatment group, SOC, PT, and total. Similar table will be provided including only ≥ 3 worst NCI CTCAE grade. TEAEs will be sorted by frequency (based on column Total of all AEs) of a SOC and the PTs within a SOC.
- The number and percentage of patients reporting study drug (pracinostat / placebo) related (as classified by investigator) TEAEs will be provided as described for “all

-

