9.2.7 Adverse events by treatment cycle

The same summary tables for adverse events described in sections 9.2.2, 9.2.3, 9.2.4 and 9.2.5 will be provided by cycle. Each AE will be assigned to only one cycle based on the date of onset. The categories in the overview summary table (number of TEAEs, NCI CTCAE grading, relationship, etc.) will be presented by treatment group and cycle.

For all the other summary tables the number and percentage of patients by treatment group, System Organ Class (SOC), Preferred Term (PT), worst NCI CTCAE grade, NCI CTCAE grade ≥ 3 , and total will be presented for each cycle. Sorting will be done as described in the relevant section. As the number of patients in higher cycle numbers may decrease, the analysis of these cycles may be not reasonable. During the BDRM it will be determined whether the analysis of cycles with a low number of patients will not be done or whether cycles will be pooled for the analysis.

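### The overall adverse-event tables have no exposure adjustment, so unequal time on open-ended treatment could move a crude arm difference by about 1 to 8 points; add exposure-adjusted rates beside them

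*SAP*

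**What the plan says.** SAP 9.2.2 builds its overall adverse-event tables from counts and percentages of patients by arm, several with the number of events added. The main table by body system and term reads: "The number and percentage of patients reporting TEAEs together with the number of AEs, will be provided by treatment group, SOC, PT, and total". SAP 9.2.3 to 9.2.5 use the same style for events leading to dose change or discontinuation, serious events and fatal serious events. SAP 9.3 repeats TEAE summaries by age, ECOG and renal function.

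The window behind each percentage has no fixed length. Protocol 3.1 says: "There is no upper limit to the number of treatment cycles administered". SAP 9.2.2 closes the window 30 days after the last pracinostat or placebo dose, or when new AML therapy starts, whichever is first.

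Three other parts of the SAP bear on time at risk:
- 9.1 summarises treatment duration, administrations and cycles by arm.
- 9.2.5 gives deaths within 30, 60 and 90 days of randomization.
- 9.2.7 repeats the adverse-event tables by cycle, each event assigned to its onset cycle. It adds: "During the BDRM it will be determined whether the analysis of cycles with a low number of patients will not be done", or whether such cycles will be pooled.

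Neither document specifies a person-time rate or a time-to-first-event analysis for adverse events.

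**The concern.** Patients stop for progression, relapse, lack of benefit, toxicity or by request (Protocol 7.1), so time at risk is an outcome that the treatment itself can change. A crude percentage mixes how often events occur per unit of time with how long patients were watched. If pracinostat keeps patients on treatment longer, its percentages rise even when it adds no toxicity per month. If it is poorly tolerated and stopped sooner, its percentages fall and real toxicity can be hidden.

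Safety and tolerability is a secondary objective, and Protocol 3.3.4 gives avoidance of bias in safety reporting as one reason for the placebo control. A comparison over windows of unequal length gives up part of that protection.

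**Working it through.** The documents give no figure for this effect, so there is none to reproduce. One input below, the design hazard ratio, belongs to a calculation that does reproduce: 390 events and "a HR of 0.714286" with the SAP's two-look boundaries give power of 90.87%, as SAP 3.3 states. That ratio describes survival, not time on treatment.

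**Inputs from the documents**
- Median 6 cycles on azacitidine alone and 6.5 on pracinostat plus azacitidine (Protocol 3.1, two separate studies).
- 28-day cycles and a 30-day tail after the last dose, so d = 30/28 cycles.
- Azacitidine Grade 3-4 rates of 28%, 26.3%, 23.7%, 19.1% and 15.7% for the five most frequent events listed in Protocol 3.3.3. These show that control incidences of 20-30% are realistic.

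**Assumptions**
- Time on treatment is exponential with stopping hazard m per cycle.
- The event hazard L is constant and, for the first table, the same in both arms.
- The new-AML-therapy limit on the window is not modelled.
- The ratio of stopping hazards is unknown. I use 6/6.5 = 0.923 (cited medians), 0.85 (intermediate), 0.714 (borrowed from the survival design) and 1/0.714 = 1.4 (opposite direction).

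**Formula.** Crude incidence = 1 − exp(−L·d) × m/(L + m), with control m = ln 2/6 = 0.1155 per cycle. L is solved to give the control incidence, then only m is changed in the other arm.

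**Worked case, control 30%.** L = 0.0422. Control: 1 − 0.9558 × 0.1155/0.1577 = 30.0%. With m × 0.714 = 0.0825: 1 − 0.9558 × 0.0825/0.1247 = 36.8%, a gap of 6.8 points.

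**Crude difference in points, identical event hazards**

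| Control incidence | ratio 0.923 | ratio 0.85 | ratio 0.714 | ratio 1.4 |
|---|---|---|---|---|
| 20% | +1.2 | +2.4 | +5.3 | −4.3 |
| 30% | +1.5 | +3.2 | +6.8 | −5.8 |
| 40% | +1.7 | +3.6 | +7.5 | −6.8 |
| 50% | +1.8 | +3.7 | +7.6 | −7.3 |

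Replacing the 6-cycle median by a control mean of 8 months, the average treatment time that Protocol 3.1 anticipates, gives nearly the same results (+5.2 to +7.6 points at an exposure ratio of 1.4, control 19.1-50%).

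**Rare and very common events.** At ratio 0.714 the gap is +3.1 points at 10% control incidence and +2.5 at 90%.

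**Early clustering.** Suppose the event hazard falls by 75% after two cycles (assumption; mean 8 months, tail left out). For control 19.1-50%, an exposure ratio of 1.4 gives +3.9 to +6.3 points and 6.5/6 gives +0.9 to +1.5.

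**Masking.** Let the true event rate be 1.4 times control and stopping 1.4 times faster. At 40% control, L = 0.0642 and 1.4L = 0.0899. The fraction m/(L + m) is unchanged at 0.6428 because both hazards are scaled equally, so only the tail differs: 1 − 0.9082 × 0.6428 = 41.6%, a gap of +1.6. With equal stopping: 1 − 0.9082 × 0.1155/0.2054 = 48.9%, a gap of +8.9. Over control 20-50% the shown difference is +0.9 to +2.0 points, against +6.1 to +9.3 at equal exposure.

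**The case against.** A reader might infer that a distortion of 5-8 points is to be expected. The documents do not support that. It needs time on treatment to scale with the survival design hazard ratio, and nothing in them says it does. The only exposure figures, 6 and 6.5 cycles, give 1-2 points, although they come from separate studies and are only indicative. The gap also shrinks for very common or rare events and when events cluster early. This part of the objection stands and sets the range given here.

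A reader might also infer that the crude difference says nothing about the drug, or that rates should replace it. Neither follows. The share of patients harmed over the treatment they actually received is a legitimate descriptive quantity, including harm accrued because benefit prolonged treatment. Safety is planned descriptively, without hypothesis tests. A single person-time rate has its own weakness: long event-free follow-up dilutes toxicity that comes early. This stands too, and is why the rates belong beside the crude tables.

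The last argument is that the SAP already covers the matter. It does so in part:
- Exposure summaries would reveal an imbalance, and event counts could be set against cycles given, but neither adjusts the patient-level percentages.
- The 30/60/90-day counts have fixed windows but cover deaths only.
- By-cycle tables give no overall comparison, do not spell out their denominator, describe selected patients in later cycles, and may be dropped or pooled where sparse.

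None supplies an overall exposure-adjusted comparison of TEAEs, serious events or events of special interest.

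**Conclusion.** The gap is real but moderate. The crude tables are incomplete, not wrong. With identical event hazards and control incidence of 20-50%, unequal time on treatment produces about 1-2 points at the cited exposure medians, 2-4 points at a stopping-hazard ratio of 0.85, and 5-8 points only if the ratio is 0.714. In the masking direction, a true 1.4-fold rate can appear as 1-2 points instead of 6-9. These sizes rest on exponential treatment duration, a constant event hazard and stopping ratios that the documents do not give. If the arms stay on treatment equally long, the effect disappears. The primary survival analysis is not touched.

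**What to change.** In SAP 9.2.2 to 9.2.5, keep the crude tables and add exposure-adjusted first-event incidence by arm for any TEAE, Grade ≥3, serious, fatal, each special-interest category and frequent preferred terms. The numerator is patients with a first event. The denominator is patient-months from first dose to that event, 30 days after the last pracinostat or placebo dose, or start of new AML therapy, whichever is earliest. Report the rate ratio with a 95% CI, and say that crude and adjusted figures are to be read together with the by-cycle tables.

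The cost is a few extra tables from onset, dosing and new-therapy dates already collected. The downside is that one rate assumes a roughly constant hazard and can dilute early toxicity; the crude and by-cycle tables remain as the check on that.

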9.2.3 Adverse events leading to dose modification and/or to discontinuation of study treatment

The number and percentage of patients reporting TEAEs leading to dose reductions, dose interruptions, and permanent discontinuation of study treatment will be tabulated in separate tables as described for “all TEAEs” in section 9.2.2. Tables related to dose reductions and dose interruptions will be additionally separated for pracinostat/placebo and AZA.

9.2.4 Serious adverse events

The number and percentage of patients reporting treatment-emergent SAEs and drug-related SAEs (study drug, AZA and either study drug or AZA) will be tabulated as described for “all TEAEs” in section 9.2.2.

9.2.5 Deaths

The number and percentage of deaths will be summarized by treatment and cause. All deaths will be additionally listed together with treatment group, dosing parameters, death date, primary cause of death and autopsy values.

Patients who died within 30 days, 60 day and 90 days from randomization will be additionally summarized.

The number and percentage of patients reporting treatment-emergent SAEs resulting in death will be tabulated by treatment group, System Organ Class (SOC) and Preferred Term (PT) (sorting for SOC and PT in alphabetical order).

9.2.6 Unblinding of treatment information

Patients where treatment information was unblinded by investigator will be listed together with treatment, date and time of unblinding.

9.2.7 Adverse events by treatment cycle

The same summary tables for adverse events described in sections 9.2.2, 9.2.3, 9.2.4 and 9.2.5 will be provided by cycle. Each AE will be assigned to only one cycle based on the date of onset. The categories in the overview summary table (number of TEAEs, NCI CTCAE grading, relationship, etc.) will be presented by treatment group and cycle.

For all the other summary tables the number and percentage of patients by treatment group, System Organ Class (SOC), Preferred Term (PT), worst NCI CTCAE grade, NCI CTCAE grade ≥ 3 , and total will be presented for each cycle. Sorting will be done as described in the relevant section. As the number of patients in higher cycle numbers may decrease, the analysis of these cycles may be not reasonable. During the BDRM it will be determined whether the analysis of cycles with a low number of patients will not be done or whether cycles will be pooled for the analysis.

9.3 SUBGROUP ANALYSES

For the following subgroups additional analyses will be performed:

- Age
 - <75 years of age at date of randomization
 - ≥ 75 years of age at date of randomization
- ECOG grade
 - 0-1 at date of randomization
 - 2 at date of randomization
- Renal impairment (Glomerular Filtration Rate (GFR)) at baseline, last value before first dose of pracinostat/placebo
 - Normal or high: ≥ 90 ml/mg/1.73m²
 - Mildly decreased: 60-89 ml/mg/1.73m²
 - Midly to moderately decreased: 45-59 ml/mg/1.73m²
 - Moderately to severely decreased: 30-44 ml/mg/1.73m²
 - Severely decreased: 15-29 ml/mg/1.73m²
 - Kidney failure <15 ml/mg/1.73m²

The GFR value is calculated depending on the gender and serum creatinine values following the table below:

Gender	Serum creatinine	GFR equation
Female	≤0.7 mg/dl (≤62 mmol/l)	$144 \times \left(\frac{SCr}{0.7}\right)^{-0.329} \times 0.993^{Age} [x 1.159 \text{ if black}]$
Female	>0.7 mg/dl (>62 mmol/l)	$144 \times \left(\frac{SCr}{0.7}\right)^{-1.209} \times 0.993^{Age} [x 1.159 \text{ if black}]$
Male	≤0.9 mg/dl (≤80 mmol/l)	$141 \times \left(\frac{SCr}{0.9}\right)^{-0.411} \times 0.993^{Age} [x 1.159 \text{ if black}]$
Male	>0.9 mg/dl (>80 mmol/l)	$141 \times \left(\frac{SCr}{0.9}\right)^{-1.209} \times 0.993^{Age} [x 1.159 \text{ if black}]$

In the case of missing demographic information (gender and/or race) the most conservative choice of parameters in the above formulas will be used (i.e. in case of missing race, 1.159 multiplier will not be used, while in case of missing gender, multiplier 141 will be used).

The following analyses will be done for each of the subgroups:

- Exposure to study drug and AZA
- Treatment Emergent Adverse Events (TEAEs)
 - Summary of TEAEs
 - Related TEAEs
 - TEAEs leading to permanent treatment discontinuation
 - Serious TEAEs
 - Related serious TEAEs
 - Serious TEAEs leading to death
 - Summary of deaths

9.4 CLINICAL LABORATORY EVALUATION ANALYSES

Clinical laboratory values (hematological panel, blood chemistry panel, and coagulation panel, as described in the clinical study protocol in section 6.2.4) will be analyzed.

Descriptive statistics will be provided for the clinical laboratory results for the SAF set by treatment cycle, as well as for the change from baseline (leukocytes differential counts expressed as percentage on leukocytes will only be listed). The baseline value is defined as the last non-missing value before the initial administration of study treatment. In addition, change from baseline will be summarized for the maximum and minimum post-baseline values and the values at the “End of Treatment” visit (or the last value obtained under treatment).

Abnormal clinical laboratory results will be graded according to NCI CTCAE version 4.03, if applicable, as graded by the Central Lab (table reported in Section 15) and the grade will be presented in the by-patient data listing. Abnormal clinical laboratory test results of NCI CTCAE grade ≥ 3 will be listed within the main laboratory data listings.

The analysis of changes compared to baseline will be done as follows:

- A shift table, presenting the 2-way frequency tabulation for baseline and the worst post-treatment value according to the NCI CTCAE grade, will be provided for all clinical laboratory parameters where NCI CTCAE grading is available.

Results of serology (HIV, HBV, HCV) examination at screening will be summarized for the ITT set and will be provided together with the baseline characteristics in the analysis.

